### **9 SAFETY REPORTING REQUIREMENTS/DATA AND SAFETY MONITORING PLAN**

#### **9.1 Definitions**

##### **9.1.1 Adverse Events**

An adverse event is defined as any reaction, side effect, or untoward event that occurs during the course of the clinical trial associated with the use of a drug in humans, whether or not the event is considered related to the treatment or clinically significant requiring treatment. For this study, AEs will include events reported by the patient, as well as new onset abnormal findings on physical examination or laboratory evaluation. A new illness, symptom, sign or laboratory abnormality outside the range of normal limits or greater than 50% increase from baseline value if the baseline is above the upper limit of normal or worsening of a pre-existing condition or abnormality is considered an AE.

All AEs, including clinically significant abnormal findings on laboratory evaluations, regardless of severity, will be followed until satisfactory resolution. AEs should be reported up to 30 days following the last dose of study drug.

An abnormal laboratory value will be considered an AE if the laboratory abnormality is characterized by any of the following:

- Results in discontinuation from the study
- Is associated with clinical signs or symptoms
- Requires treatment or any other therapeutic intervention
- Is associated with death or another serious adverse event, including hospitalization.
- Is judged by the Investigator to be of significant clinical Impact

If any abnormal laboratory result is considered clinically significant, the investigator will provide details about the action taken with respect to the test drug and about the patient's outcome.

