### 3.6 Study Calendar

The timing of study events in the following descriptions is relative to the administration of EOVIST®.

Procedure	Screening a	Baseline b	MR imaging			Scheduled Post-MRI c
			Just prior to MRI	Pre-injection MRI scan	Post injection MRI scan	
Informed consent	X					
Study entry criteria	X					
Demographic information	X					
Medical history and concurrent diseases	X					
Prior/concomitant medications	X					
Injection site monitoring				X	X d	X
Vital signs	X	X			X e	
Acute Care Panel, Hepatic Panel, Mineral Panel, PSA, & CBC	X f					
OATP1B3 Genotype analysis	X g					
Biopsy specimen available for OATP1B3 expression	X h, i					
Intravenous line started			X			
Eovist® injection				X		
Adverse Event Monitoring			X	X	X	X
MR Imaging				X	X j	
Biopsy Procedure						X k, l
Prostatectomy						X m
OATP expression and Comparative Analyses						X

a: Within 21 days of administrations of Eovist®

b: The day of MR imaging until just prior to administration of Eovist ®

- c. Timing of events is relative to administration of Eovist®
- d: 5 minutes post-Eovist® injection
- e: At the end of all scanning
- f: Clinical blood sample assessments must be performed within 21 days prior to administration of Eovist®.
- g: Will be performed at [name] Lab.
- h: For the localized disease arm, existing pathologic tissue (obtained <20 weeks before Eovist MRI) will be screened to see if it can be linked to MRI visible lesion in the patient candidate for Eovist MRI. Otherwise the tissue obtained from image guided biopsy (standard of care) at NCI will be used for OATP1B3 expression.
- i: For the advanced disease arm, availability of the previously (<20 weeks) obtained clinically acquired tissue will be checked.
- j: Immediately, 10, 20, & 60 minutes post-Eovist® injection
- k: To be conducted within <20 weeks after Eovist® enhanced MRI
- l: This applies for the advanced disease arm and will be conducted from a soft tissue or metastatic bone lesion (measuring  $\geq 1.5\text{cm}$  in diameter).
- m: This applies for the localized disease arm and will serve as a source of tissue only if previously acquired biopsy (confidently linked to an MRI visible lesion) or image guided standard of care biopsy at NCI will not be available.

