### **3.6.1.3 MR Imaging Period**

Prior to entering the MRI scanner the patient will answer the standard MRI safety checklist administered to all patients undergoing MRI in the Clinical Center to insure that it is safe to perform an MRI. The patient will be placed into the magnet in supine position and an intravenous line will be placed. A 32 channel cardiac coil will be used for MR imaging. An endorectal coil will be used for localized disease arm.

The following scans will be obtained:

- Scout view of the pelvis to check positioning of the cardiac coil.
- T1 weighted MRI of abdomen and pelvis.
- T2 weighted MRI of abdomen and pelvis.
- Total nominal time: 40 minutes +/- 5 minutes for setup and clean-up +/- 10 minutes in case any sequence needs to be repeated due to unforeseen events such as patient motion during imaging acquisition. At any given time the patient will be required to lie still for 5-7 minutes.

After completion of the pre-injection MRI scan, patient will have the Eovist® injection as detailed above in section [3.3](#). The patient will be assessed for adverse events 15 minutes post-Eovist® Injection and if they are stable, the same MR imaging protocol (except for the scout view) specified above will be performed immediately after injection and at approximately 10th, 20th and 60th minute time points after injection with the same MRI set up.

Following imaging acquisition, the data will be transferred to the clinical PACS system for storage.

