### **3.6.1.4 Post-Eovist® Enhanced MR Imaging Period**

A final set of vital signs and AE assessment will be performed at the end of the 60 minute MRI scan.

Within 20 weeks of the Eovist® enhanced MRI the biopsy procedure will be performed.

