## 5 DATA COLLECTION AND EVALUATION

### 5.1 Data Collection

#### 5.1.1 Clinical Data

All data will be kept secure. Personal identifiers will not be used when collecting and storing data. An enrollment log will be maintained in the regulatory binder/file which is the only location of personal identifiers with unique subject identification number.

Clinical data including summary and demographic data will be collected and entered into NCI CCR Database, C3D. Adverse events occurring during any scanning session will be recorded. Adverse events which are designated possibly, probably or definitely related to Eovist® will also be recorded.

Imaging data will include storage of the reconstructed images and image derived parameters on a secure, password protected lab imaging database. The lab imaging database will be stored

and maintained in the Molecular Imaging Program facilities. Personal identifiers will not be used when storing data.

Non-Anonymized images may also be stored in the clinical center PACS.

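### Adverse events are to be reported for 30 days after the dose, but no check after the end of the 60-minute scan has a date

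*Combined protocol and SAP*

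**What the plan says.** Section 9.1.1 sets the window: "AEs should be reported up to 30 days following the last dose of study drug". It defines an adverse event as something that counts "whether or not the event is considered related to the treatment", and adds: "For this study, AEs will include events reported by the patient". Under section 3.3 each subject receives one injection, so the clock starts on the MRI day.

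Two adverse-event checks have a stated time. Section 3.6.1.3 has the first: "The patient will be assessed for adverse events 15 minutes post-Eovist® Injection". Section 3.6.1.4 has the second: "A final set of vital signs and AE assessment will be performed at the end of the 60 minute MRI scan". The calendar in 3.6 also ticks the row "Adverse Event Monitoring" in the Scheduled Post-MRI column. The footnote to that column says only "Timing of events is relative to administration of Eovist".

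On recording, section 5.1.1 says "Adverse events occurring during any scanning session will be recorded" and adds events judged at least possibly related to Eovist. Section 5.1.2 collects adverse events according to the calendar with no relatedness condition, and collects serious events over a follow-up period whose length is not given. Section 3.9 takes subjects off study when their procedures are finished. Section 9.2.2 lists what goes to the IRB at continuing review.

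**The concern.** A reporting window is only as good as the contacts that fill it. Here the window is 30 days, and the checks with a time attached end on the imaging day. The gap matters because section 10.2.2 says that hypersensitivity reactions to Eovist can appear hours to several days later, which is after the last timed check.

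Two things depend on those events being found. One is the safety summary of the study. The other is the stopping rule in 9.3.1, which ends the study if three subjects have Eovist-related serious events of grade 2 or higher. A delayed reaction that is serious and related counts toward that rule only if someone learns of it.

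There is also a wording risk. Staff who work from 5.1.1 alone could take it as the full recording rule and leave out an unrelated event on, say, day 10, which 9.1.1 treats as reportable.

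**Working it through.** There is no figure in the plan to reproduce. The check compares the sections, with a little arithmetic on scale.

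1. **Window.** 30 days × 24 = 720 hours, or 43,200 minutes, counted from the single dose (9.1.1, 3.3).

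2. **Timed checks.** 15 minutes (3.6.1.3) and the end of the 60-minute scan (3.6.1.4). Taking 60 minutes as the time of the second check, 60 / 43,200 = 0.14% of the window has passed. The length of that scan adds to this, but even a further hour (an assumption) gives 120 / 43,200 = 0.28%.

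3. **Undated check.** The calendar's end-of-scanning vital signs sit in the post-injection column (footnote e). This suggests that the Scheduled Post-MRI tick is a further, later check. No day is attached to it. The only timed item in that column is the biopsy, allowed up to 20 weeks after the MRI (footnote k): 20 × 7 = 140 days, of which 140 − 30 = 110 lie outside the window. A biopsy visit may therefore fall within 30 days, but need not.

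4. **Subjects with no later visit.** Footnotes h and i allow tissue obtained before the MRI. Such a subject may need no later biopsy, and 3.9 then permits him to go off study with no hold to day 30.

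5. **Recording rules side by side.**
   - 9.1.1: all adverse events to day 30, related or not.
   - 5.1.2: adverse events per the calendar, no relatedness condition. Serious events are covered by two overlapping bullets, one without and one with a causality condition, over an undefined follow-up period.
   - 5.1.1: events in scanning sessions and, in addition, events related to Eovist. This is narrower than the other two, but contains no exclusion.
   - 9.2.2: a selection for an IRB table. It does not say what is recorded.

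6. **Can the number missed be estimated?** Section 10.2.2 cites a 4.3% adverse-reaction rate. Expected subjects with any reaction = n × 0.043: 20 × 0.043 = 0.86 with the 20 subjects of section 3.1, and 25 × 0.043 = 1.08 with the 25 of section 7.1. The chance of at least one is 1 − 0.957^20 = 58% to 1 − 0.957^25 = 67%. The chance of two or more is 1 − 0.957^n − n × 0.043 × 0.957^(n−1), which is 21% (n = 20) to 29% (n = 25). These figures do not measure the gap. They include reactions during the attended scan, the rate was collected over 24 hours for most subjects, and the share starting after the last timed check is not given. Section 10.2.2 also puts most hypersensitivity reactions within the first half hour.

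7. **Serious reactions.** Section 10.2.2 gives a rate below 0.5%, so fewer than 25 × 0.005 = 0.125 subjects are expected, whatever the timing. This assumes that the cited rate carries over to these patients.

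**The case against.** The best reply is that a reporting window is not a visit schedule. Section 9.1.1 counts events that the patient reports, so passive reporting to day 30 is coherent for one dose of an approved agent, and safety is not a study objective. There are safeguards too: adverse events are followed to resolution (9.1.1), subjects with unacceptable toxicity may not leave until it settles (3.9.1), monitoring continues after withdrawal for a clinical adverse event (3.9), and the investigator reviews each patient's data (9.3.1). Consent pages are not in the public text and may tell subjects whom to call.

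Much of this stands, and it limits the weight of the point. But the safeguards act on events already known. They do not bring a new delayed event to light, and nothing visible prompts the subject to report one.

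Three stronger readings are tempting and should not be drawn:

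- A reader might infer that nothing is planned after the scan. The calendar ticks a post-MRI check; what it lacks is a date.
- A reader might infer that 5.1.1 forbids recording unrelated events outside scanning. Its two sentences are additive, and 5.1.2 has no such filter, so a conflict is implied at most.
- A reader might infer that 9.2.2 is another conflicting recording rule. It is an IRB summary list, a narrower list of that kind is normal, and it contradicts neither 5.1.1 nor 5.1.2.

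**Conclusion.** The point holds in a limited form. Followed as written, the plan does not actively cover its own 30-day window: the last timed check is about an hour after the dose, the later check has no day, the follow-up period has no length, and a subject with existing tissue can leave after the MRI. Section 5.1.1 is also worded more narrowly than 9.1.1 and 5.1.2.

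The number of events at risk cannot be estimated from the documents. It is likely small, since most hypersensitivity reactions fall inside the attended period. A reader might take the expected count of about one subject as a ceiling on what could be missed. It is not: it is a mean, two or more reactors have a 21% to 29% chance, and a mostly 24-hour rate cannot bound reactions that begin days later.

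The imaging endpoint is unaffected. With serious reactions so rare, a missed event is unlikely to change the outcome of the three-subject stopping rule. This is a cheap improvement to safety ascertainment. The conclusion rests on the visible text and assumes that no dated contact is set out in the pages that were removed.

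**What to change.** - In the 3.6 calendar, date the Scheduled Post-MRI adverse-event check: one telephone contact within a few days of the dose, to match the delayed-reaction period, and one at day 30.
- In 3.6.1.4, stop describing the end-of-scan adverse-event assessment as final.
- In 5.1.2, define the follow-up period as 30 days after Eovist.
- In 3.9, keep subjects on study until the day-30 contact is made.
- In 5.1.1, state that all adverse events through day 30 are recorded regardless of relatedness, in line with 9.1.1.
- Leave 9.2.2 as it is.

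The cost is protocol wording and, for 25 subjects, 25 × 1 = 25 to 25 × 2 = 50 short calls by existing staff, depending on whether one or both contacts are adopted. Some subjects would stay on study longer than now, up to day 30. No new procedure is needed.

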#### **9.1.2 Suspected adverse reaction**

Suspected adverse reaction means any adverse event for which there is a reasonable possibility that the drug caused the adverse event. For the purposes of IND safety reporting, 'reasonable possibility' means there is evidence to suggest a causal relationship between the drug and the adverse event. A suspected adverse reaction implies a lesser degree of certainty about causality than adverse reaction, which means any adverse event caused by a drug.

#### **9.1.3 Unexpected adverse reaction**

An adverse event or suspected adverse reaction is considered "unexpected" if it is not listed in the investigator brochure or is not listed at the specificity or severity that has been observed; or, if an investigator brochure is not required or available, is not consistent with the risk information described in the general investigational plan or elsewhere in the current application. "Unexpected", also refers to adverse events or suspected adverse reactions that are mentioned in the investigator brochure as occurring with a class of drugs or as anticipated from the pharmacological properties of the drug, but are not specifically mentioned as occurring with the particular drug under investigation.

#### **9.1.4 Serious**

An Unanticipated Problem or Protocol Deviation is serious if it meets the definition of a Serious Adverse Event or if it compromises the safety, welfare or rights of subjects or others.

#### **9.1.5 Serious Adverse Event**

An adverse event or suspected adverse reaction is considered serious if in the view of the investigator or the sponsor, it results in any of the following:

- Death,
- A life-threatening adverse drug experience
- Inpatient hospitalization or prolongation of existing hospitalization

- Persistent or significant incapacity or substantial disruption of the ability to conduct normal life functions
- A congenital anomaly/birth defect.
- Important medical events that may not result in death, be life-threatening, or require hospitalization may be considered a serious adverse drug experience when, based upon appropriate medical judgment, they may jeopardize the patient or subject and may require medical or surgical intervention to prevent one of the outcomes listed in this definition.

#### **9.1.6 Disability**

A substantial disruption of a person's ability to conduct normal life functions.

#### **9.1.7 Life-threatening adverse drug experience**

Any adverse event or suspected adverse reaction that places the patient or subject, in the view of the investigator or sponsor, at immediate risk of death from the reaction as it occurred, i.e., it does not include a reaction that had it occurred in a more severe form, might have caused death.

#### **9.1.8 Protocol Deviation (NIH Definition)**

Any change, divergence, or departure from the IRB approved research protocol.

#### **9.1.9 Non-compliance (NIH Definition)**

The failure to comply with applicable NIH Human Research Protections Program (HRPP) policies, IRB requirements, or regulatory requirements for the protection of human research subjects.

#### **9.1.10 Unanticipated Problem**

Any incident, experience, or outcome that:

- Is unexpected in terms of nature, severity, or frequency in relation to
  - a) the research risks that are described in the IRB-approved research protocol and informed consent document; Investigator's Brochure or other study documents, and
  - b) the characteristics of the subject population being studied; **AND**
- Is related or possibly related to participation in the research; **AND**
- Suggests that the research places subjects or others at a *greater risk of harm* (including physical, psychological, economic, or social harm) than was previously known or recognized.

### **9.2 NCI-IRB Reporting**

#### **9.2.1 NCI-IRB Expedited Reporting of Unanticipated Problems and Deaths**

The Protocol PI will report to the NCI-IRB:

- All deaths, except deaths due to progressive disease
- All Protocol Deviations

- All Unanticipated Problems
- All serious non-compliance

Reports must be received by the NCI-IRB within 7 working days of PI awareness via iRIS.

### **9.2.2 NCI-IRB Requirements for PI Reporting of Adverse Events at Continuing Review**

The protocol PI will report to the NCI-IRB:

1. A summary of all protocol deviations in a tabular format to include the date the deviation occurred, a brief description of the deviation and any corrective action.
2. A summary of any instances of non-compliance
3. A tabular summary of the following adverse events:
  - All Grade 2 **unexpected** events that are possibly, probably or definitely related to the research;
  - All Grade 3 and 4 events that are possibly, probably or definitely related to the research;
  - All Grade 5 events regardless of attribution;
  - All Serious Events regardless of attribution.

## **9.3 Data and Safety Monitoring Plan**

### **9.3.1 Principal Investigator/Research Team**

The Principal Investigator and Research Nurse will monitor the study for AEs.

This study will not have a formal data safety monitoring plan (DSMP), however, the Principal Investigator and Lead Associate Investigator will re-evaluate the protocol after each patient.

The principal investigator reserves the right to terminate the study on safety grounds. If 3 study subjects experience  $\geq$  grade 2 Eovist®-related SAEs then the study will be terminated. Before terminating the study, the investigator will ensure that a review of the overall risk/benefit analysis confirms the balance to be no longer acceptable. Should termination be necessary, the investigator will arrange the relevant procedures, which will include informing the IRB, and other relevant local and national authorities. On termination of the study, the investigator will assure that adequate consideration is given to the protection of enrolled subjects' interests. Termination of the study will be considered in the event of significant safety findings occurring at any time during the performance of the study.

Adverse events will be reported as required above. Any safety concerns, new information that might affect either the ethical and or scientific conduct of the trial, or protocol deviations and violations will be immediately reported to the IRB using iRIS.

The principal investigator will review adverse event and response data on each patient to ensure safety and data accuracy. The principal investigator will personally conduct or supervise the investigation and provide appropriate delegation of responsibilities to other members of the research staff.

## 10 PHARMACEUTICAL INFORMATION

### 10.1 Eovist® Source

Eovist® is an FDA approved pharmaceutical and it is commercially available from Bayer Pharmaceuticals, Inc.

### 10.2 Toxicity

#### 10.2.1 Pharmacology and Toxicology in Animals

A dose-related increase in QT interval corrected for heart rate (QTc) which was resolved by 30 minutes post dosing was observed in dogs when given a single dose of Eovist®. The increase was noted when given in doses equal to or greater than 0.1 mmol/kg (2.2 times the human dose). Maximum increase in QTcF was equal to or less than 20 ms at doses up to 0.5 mmol/kg (11 times the human dose). A gait disturbance was observed in 1 of 3 mice when given Eovist® at a dose of approximately 1.1 mmol/kg (3.6 times the human dose); the disturbance occurred at 30 minutes post dosing and resolved at 4 hours post dosing.

#### 10.2.2 Toxicity in Humans

Toxicities are not anticipated in this study. In the event that a patient experiences an allergic reaction, or toxicity greater than grade 2 during the Eovist® injection, the injection will be stopped immediately and standard supportive measures instituted. No further Eovist® will be administered.

Overall, 4.3% of subjects reported one or more adverse reactions during a follow-up period that for most subjects, extended 24 hours after Eovist® administration. The reported AEs of Eovist® were feeling hot (0.9%), nausea (0.6%), headache (0.5%), injection site reactions, the reported serious reaction rate is less than 0.5% [6].

Gadolinium-based contrast agents (GBCAs) increase the risk for nephrogenic systemic fibrosis (NSF) among patients with impaired elimination of the drugs. The GBCA-associated NSF risk appears highest for patients with chronic, severe kidney disease (GFR <30 mL/min/1.73m^2) as well as patients with acute kidney injury. The risk appears lower for patients with chronic, moderate kidney disease (GFR 30–59 mL/min/1.73m^2) and little, if any, for patients with chronic, mild kidney disease (GFR 60-89 mL/min/1.73m^2). NSF may result in fatal or debilitating fibrosis affecting the skin, muscle and internal organs [6].

Anaphylactoid and anaphylactic reactions with cardiovascular, respiratory and cutaneous manifestations, ranging from mild to severe reactions, including shock have uncommonly occurred following Eovist® administration. Most hypersensitivity reactions to Eovist® have occurred within half an hour after administration. Delayed reactions (hours up to several days) may occur [6].

